Quantitative analysis of the participatory ranking exercise: Each participant's responses will be used to generate an individualized weighted composite outcome. We will consider a utility function that is a weighted combination of the individual endpoints specified by each participant, with weights determined by the patient's preferences as proposed in Butler et al.¹⁶ The patient's preference weights will be scaled to sum to 1, such that the patient-specific outcome will be a convex combination of the eligible outcomes. With the weighted utility function, we then define potentially counterfactual treatment effects, defined as the expected utility function under the four different treatment exposures. The optimal individual treatment rule is defined as in Qian and Murphy¹⁷ as the treatment that maximizes the expected utility function.

We will then use the composite outcomes generated using the participator ranking exercise (see above) in a study that uses de-identified data within OLDW. Specifically, we will emulate a target trial comparing the effectiveness of GLP1-RA, SGLT2i, DPP-4i, and SU classes with respect to each of these patient-specified composite outcomes. The target parameter will be the six pairwise differences in the personalized utility function between the drug classes. We provide an overview of that analysis below, though all analyses using

OLDW data have been previously deemed exempt from IRB review as all data is statistically de-identified by OptumLabs prior to being made available to researchers.

Primary analyses will be conducted under an intention-to-treat approach, modified to define “intention” as a patient having two consecutive fills of the assigned drug. All patients will continue follow-up and complete all outcome assessments until the planned conclusion of the study or end of observation in OLDW.

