We will estimate multinomial propensity score models using data from 12 months prior to the index date to account for the multiple treatments.¹⁸ Predictions from the estimated propensity score model can be used for inverse probability weighting (IPW) to emulate baseline randomization. We will allow for flexible modeling strategies with controls to assess for overfitting. Our proposal is to use the super learner framework¹⁹ with a diverse set of individual prediction algorithms included in the ensemble. The super learner framework allows for flexible estimation of an ensemble predictor with the theoretical properties of cross-validation for model selection to control for overfitting. The framework has been demonstrated to outperform individual algorithms for the estimation of propensity scores.^{20,21} The distribution of the predicted propensity scores will be evaluated for evidence of violations of the positivity assumption. For moderate violations of positivity, the propensity scores will be truncated at 0.01 and 0.99 to control inflation of the standard errors. Our intention is to use the entire distribution of OLDW as our population of interest, but if more extreme positivity violations are observed, the reference population will be narrowed to a realistic treatment intervention population.

The proposed IPW weight with multinomial treatment groups is unstabilized, as our primary estimand is the population average treatment effect.²² If weights have extreme values when evaluating the distributions, then the stabilized version using the denominator proposed in Yoshida²³ for the optimal matching stabilized weights with multiple treatments will be used as a sensitivity analysis to avoid large confidence intervals for the effect estimates. The final propensity scores will then be incorporated as IPWs into a time-to-event model. If the proportional hazards assumptions hold, this will be a Cox model; otherwise, we will use Akaike Information Criteria to identify the best parametric time-to-event specification for the data. For the final model, we will report model diagnostic and performance statistics, and either hazard or time ratios with 95% confidence intervals. A single model with all treatment groups will be estimated and the omnibus test for at least one treatment group having a different cumulative incidence rate will be evaluated. If that test is statistically significant, then each pairwise comparison will be tested and pairwise effects estimated.

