A secondary analysis will be conducted under an as-treated approach, whereby patients will be censored upon discontinuation of the assigned treatment (no fills after 30 days beyond the dispensed pill count) or addition of another drug (i.e. another 2nd-line drug or insulin). To adjust for the likely informative censoring post-baseline, time-dependent propensity score models will be estimated and applied to dynamically reweight the population and account for time-varying confounding and informative loss to follow-up. The time-dependent propensity score models will be based on all prior covariate information up to that time point. This will address two concerns with use of observational methods for comparative effectiveness, immortal time bias⁴⁴ and time-lag bias,⁴⁵ as we will allow for time-dependent exposures and reweighting on time-conditional propensity scores.⁴⁶

Qualitative analysis of the accompanying interview: Interviews will be transcribed and analyzed according to a general thematic analysis approach (Braun & Clark, 2012) to identify patterns of meaning across patient interviews.

REFERENCES

1. CDC. National Diabetes Statistics Report, 2020. In. Atlanta, Georgia, U.S.A.: U.S. Department of Health and Human Services, Centers for Disease Control and Prevention; 2020.
2. American Diabetes Association Standards of Medical Care in Diabetes—2020. Section 9. Pharmacologic Approaches to Glycemic Treatment. *Diabetes Care*. 2020;43(Supplement 1):S98-S110.
3. NICE. National Institute for Health and Care Excellence Pathways: Managing Blood Glucose in Adults with Type 2 Diabetes. National Institute for Health and Care Excellence. <https://pathways.nice.org.uk/pathways/type-2-diabetes-in-adults>. Published 2019. Updated March 26, 2019. Accessed April 23, 2019.

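### The average-effect estimand is no reason to leave the weights unstabilized; weights summing to about 4N under-penalize AIC and require a named weight-aware variance

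*Combined protocol and SAP*

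**What the plan says.** All of this is in the combined protocol and SAP, under Data Analysis Plan, in the part on the claims-data emulation.

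- **Comparison.** It concerns four drug classes ("comparing the effectiveness of GLP1-RA, SGLT2i, DPP-4i, and SU classes"), and "The target parameter will be the six pairwise differences in the personalized utility function between the drug classes".
- **Weight and reason.** "The proposed IPW weight with multinomial treatment groups is unstabilized, as our primary estimand is the population average treatment effect". No formula is given. I read the weight as one over the estimated probability of the patient's own class given covariates.
- **Handling of extreme scores and weights.** For moderate positivity violations, "the propensity scores will be truncated at 0.01 and 0.99 to control inflation of the standard errors". If weights are extreme, a stabilized version is offered, but it is the matching weight: the denominator proposed "for the optimal matching stabilized weights with multiple treatments will be used as a sensitivity analysis to avoid large confidence intervals".
- **Use of the weights.** They go into a Cox model if proportional hazards holds; "otherwise, we will use Akaike Information Criteria to identify the best parametric time-to-event specification for the data". The plan will report "either hazard or time ratios with 95% confidence intervals". An omnibus test across the four classes opens the pairwise comparisons.
- **Targeted learning.** The next paragraph adds targeted-learning estimates of the four hazard rates, an omnibus test at 0.05 and Holm-adjusted pairwise p-values.
- **As-treated analysis.** "time-dependent propensity score models will be estimated and applied to dynamically reweight the population", with no weight form stated.

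Nowhere does the plan name a sandwich, bootstrap or influence-function variance, or say that weights are rescaled to N before a likelihood, AIC or test is computed.

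**The concern.** The plan gives the estimand as its reason for not stabilizing, as if stabilizing would change the estimand. Stabilizing by the marginal class share does not; switching to matching weights does. The plan treats the two as one.

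The choice affects scale. Unstabilized weights inflate the apparent size of the cohort, and any quantity computed from the weighted likelihood as if weights were patient counts inherits that inflation. AIC is such a quantity. Model-based standard errors and an unscaled weighted likelihood-ratio test would be too, if they were used. At stake are the choice of parametric form when proportional hazards fails, the width of the intervals, the test that opens the pairwise comparisons, and precision in the as-treated analysis.

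**Working it through.** **Inputs.** From the plan: K = 4 classes, unstabilized weights, truncation at 0.01 (largest weight 1/0.01 = 100), omnibus level 0.05. The six pairwise contrasts agree with 4 × 3 / 2 = 6. The plan gives no cohort size, class shares, event rates or stopping rates for this analysis, so those below are assumptions.

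**1. Does stabilizing change the target?** For class *a* with share p_a and score e_a(X), the weights are 1/e_a(X) and p_a/e_a(X). Their ratio, p_a, is the same for every patient in the class, so the weighted covariate distribution within the class is unchanged. In a Cox model the target is exactly the same under proportional hazards; otherwise the averaged hazard ratio can depend on class shares. In simulation (N = 3,000, 1,500 runs per scenario, fitted multinomial scores truncated as planned, no treatment effect) the log hazard ratios differed by at most 0.0008 on average.

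**2. Total weight.** In each class the expected sum of 1/e_a(X) is N, so the total is K × N = 4N (simulated 3.997N to 4.000N after truncation). Per class the over-count is 1/p_a: 4 in each at equal shares, but 10.0, 6.7, 3.3 and 2.2 at assumed shares 0.10/0.15/0.30/0.45.

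**3. AIC.** One extra nested parameter is kept if the likelihood-ratio statistic exceeds 2. At equal shares the weighted statistic is about four times its proper value, so the effective threshold is 2/4 = 0.5.
- Proper scale: P(χ²₁ > 2) = 0.16.
- Unstabilized: P(χ²₁ > 0.5) = 0.48.
- Simulated, exponential truth with Weibull as the needless alternative: 0.47 unstabilized against 0.16 stabilized at equal shares; 0.58 against 0.17 at shares of about 0.11/0.14/0.28/0.47.

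A sandwich variance does not touch this, because AIC uses the weighted likelihood itself.

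**4. Intervals and omnibus test, if the variance is model-based.** At equal shares the model-based variance is a quarter of the true one.
- Coverage: P(|Z| < 1.96/2) = 0.67 (simulated 0.675).
- Omnibus rejection under the null, 3 df: P(χ²₃ > 7.815/4 = 1.954) = 0.58 (simulated 0.57).
- Unequal shares: pairwise variance is understated by (1/p₁ + 1/p₂)/2. For 0.30 and 0.45 this is (3.33 + 2.22)/2 = 2.8; for 0.10 and 0.15 it is (10 + 6.67)/2 = 8.3.

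Simulated omnibus type I error and interval coverage:

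| Weights and variance | Equal shares, no confounding | Unequal shares, confounded |
|---|---|---|
| Unstabilized, model-based | 0.57; 0.675 | 0.73; 0.46 |
| Stabilized, model-based | 0.05; 0.95 | 0.10; 0.88 |
| Either, sandwich | 0.05; 0.95 | 0.04; 0.95 |

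Over all scenarios the sandwich gave type I error of 0.03 to 0.05 and coverage of 0.94 to 0.96 with either weight.

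**5. As-treated analysis, if its weights are unstabilized.** Assume rare events at a constant rate, stopping unrelated to covariates and equal in the classes compared, and a fraction *s* stopping per year, so that c = −ln(1 − s) and the probability of remaining on treatment is G(t) = exp(−ct). Over T years the variance is proportional to ∫(1/G)dt / T² with weight 1/G, and to 1/∫G dt with stabilized weight 1. The ratio is 2[cosh(cT) − 1]/(cT)².

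| Stopping per year | 2 years | 3 years | 5 years |
|---|---|---|---|
| 30% (c = 0.357) | 1.04 | 1.10 | 1.29 |
| 50% (c = 0.693) | 1.17 | 1.42 | 2.50 |

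For example, at 50% over 5 years cT = 3.466 and cosh(cT) = 16.016, so the ratio is 2 × 15.016/12.011 = 2.50. This loss remains when the variance is estimated correctly.

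**The case against.** A reader might infer that, as written, the intervals and the omnibus test count the cohort four times over. The documents do not support that. It requires a model-based variance or an unscaled weighted likelihood-ratio test, and the plan specifies neither. The text leans the other way: the authors expect extreme weights to inflate standard errors and widen intervals, whereas a variance that treats weights as counts shrinks as weights grow. The plan calls this part an overview, and silence on the variance there would by itself be missing detail. The omnibus test with the stated 0.05 level follows the targeted-learning estimates, which need not use the weighted model's variance. All of this stands, and it makes the interval and omnibus figures conditional.

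A reader might also infer that the as-treated weights are unstabilized. The sentence on unstabilized weights concerns the baseline multinomial weight, and the as-treated paragraph gives no form. That part is conditional too.

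The AIC effect is narrow. It arises only if proportional hazards fails, the penalty cancels between forms with equal numbers of parameters, and in a large claims cohort clear likelihood differences would dominate. This limits the practical effect but does not correct the scale.

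The estimand sentence can be read charitably as inverse probability weights against matching weights, which is a valid distinction. As worded, though, it excludes the stabilized weight that keeps the estimand. Finally, once a sandwich variance is used, stabilizing the baseline weights changes essentially nothing in the primary intervals. That is true, and it is why the variance must be named and stabilizing alone is not offered as the remedy.

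**Conclusion.** The stated reason for leaving the weights unstabilized does not hold, whatever variance is used. The AIC consequence follows from the weights as stated if AIC is taken, as the text reads, from the weighted likelihood without rescaling: about a quarter of the proper penalty overall, and 48% against 16% retention of a needless parameter at equal shares. Its practical effect may be small in a large cohort.

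The 67% coverage and 58% null rejection hold only for a model-based variance at equal shares with no weight variation within class. The as-treated variance ratio of 1.04 to 2.5 holds only if the unstabilized form is carried over, under the assumed stopping rates and follow-up and with stopping unrelated to covariates. Fourfold describes the total; each class is over-counted by one over its share. The point is worth acting on because it changes a stated choice at almost no cost, not because the plan has adopted an invalid test.

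**What to change.** 1. Make class share divided by propensity score the primary weight. Rescaling the unstabilized weights to sum to N before AIC is a weaker alternative: it corrects the total but leaves each class at 1/(4 × share) of its true size, for example 2.5, 1.7, 0.8 and 0.6 at shares 0.10/0.15/0.30/0.45.
2. State a robust sandwich variance, or a patient-level bootstrap that refits the scores, for all weighted-model intervals, and use a Wald omnibus test based on it. Stabilizing without this left type I error at 0.10 and coverage at 0.88 with unequal, confounded classes.
3. In the as-treated analysis, state the weight form and put the class-specific probability of remaining uncensored to that time in the numerator.
4. Delete the statement that ties unstabilized weights to the average-effect estimand. If matching weights stay as a sensitivity analysis, say that they target a different population.

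The cost is a few lines of SAP text and code. Hazard ratios are essentially unchanged under proportional hazards. Without it, the averaged hazard ratio can shift slightly, and a different AIC choice would change the parametric estimates.

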The targeted learning algorithm for the causal hazard rate as defined in Moore and van der Laan²⁴ will be implemented to estimate the four treatment hazard rates and the corresponding hazard ratios or time ratios, according to the model specification, will be estimated for each of the 6 pairwise comparisons between treatment groups. A single overall omnibus test for the four hazard rates being equal to each other versus at least one different will be conducted at the 0.05 significance level, with pairwise comparison p-values adjusted using the Holm closed sequential multiple testing procedure.^{25,26}

Predefined subgroup analyses for heterogeneity of treatment effects (HTE) will be evaluated for the following characteristics: sex (female vs. male), race/ethnicity (Black, Hispanic, Asian, other vs. White), and age (45-64, 65-74, ≥ 75 vs. <45 years). While there is no definitive evidence of HTE by these characteristics, the incidence of CVD and kidney disease outcomes are known to vary²⁷⁻³⁰ and may be mediated by different responses to therapeutic interventions. We will also assess for HTE as a function of different levels of underlying CVD risk, as the examined drugs may be more effective at reducing the risks of primary and secondary endpoints among patients at higher risk for these events or with certain CVD risk factors already present.^{31-35 36-39} The primary model will be used to estimate treatment effects across subgroups, with the targeted parameter for the subgroup analysis being the difference in the predicted treatment effect for each pairwise comparison between the

subgroups.⁴⁰ We will estimate multivariable effect prediction models^{41,42} to assess for HTE between the predefined subgroups by incorporating specific parameters for the statistical interaction effect between the treatment and subgroup variables.^{36,37} Propensity score weights will be used to emulate randomization according to the target trial framework. Internal cross-validation will be used to control for overfitting of the prediction model.⁴³ Adjustment for multiple testing will be done accounting for the total number of predefined HTE analyses.

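### If proportional hazards fails, the AIC fallback does not target that failure and makes the effect scale depend on the data; separately, neither scale is the declared utility difference

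*Combined protocol and SAP*

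**What the plan says.** All of this is in the Data Analysis Plan of the combined protocol and SAP, under the quantitative analysis of the participatory ranking exercise.

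- **Composites.** "Each participant's responses will be used to generate an individualized weighted composite outcome". The four drug classes are then compared "with respect to each of these patient-specified composite outcomes". Target accrual is 25, so there are up to 25 composites.
- **Target.** "The target parameter will be the six pairwise differences in the personalized utility function between the drug classes". The treatment effects are defined through expected utility, with preference weights that sum to 1.
- **Model.** After inverse probability weighting, the first choice is conditional: "If the proportional hazards assumptions hold, this will be a Cox model". The fallback when that condition fails is stated as follows: "otherwise, we will use Akaike Information Criteria to identify the best parametric time-to-event specification for the data". No proportional-hazards test or threshold is given, and no list of candidate models.
- **Reporting.** For the final model, "we will report model diagnostic and performance statistics, and either hazard or time ratios with 95% confidence intervals". The targeted-learning step follows the same choice: "the corresponding hazard ratios or time ratios, according to the model specification, will be estimated for each of the 6 pairwise comparisons". The primary model is also reused for the subgroup analyses.

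**The concern.** Two separate problems meet here.

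First, the fallback is triggered by a treatment effect that is not proportional over time, but the rule that picks the replacement does not look for a model that allows such an effect. The analysis can end with a model that makes the assumption just rejected, or one that makes an equally rigid assumption on the time scale. Which of these occurs, and whether a hazard ratio or a time ratio is reported, is settled by the data.

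Second, whichever model is used, the reported number is a ratio, while the declared target is a difference in expected utility. The optimal treatment rule is defined as the class that maximises expected utility, so that is the quantity the study needs. Followed as written, the plan does not deliver it.

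**Working it through.** The plan gives no sample size, event rate or power for the claims analysis, so there is no figure of its own to reproduce. The one count available checks: four classes give 4 × 3 / 2 = 6 pairs.

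**1. What the candidate models assume.** With one shape *k* shared by all arms, the Weibull hazard in arm *a* is k·t^(k−1)·exp(α + β_a). The ratio between arms *a* and *b* is exp(β_a − β_b), which does not involve *t*: proportional hazards. The exponential is the case k = 1. A Weibull time ratio equals HR^(−1/k), so quoting a time ratio does not show that proportional hazards was avoided. Log-normal and log-logistic models with a common shape have log T = μ + γ_a + σε, so one time ratio exp(γ_a − γ_b) applies throughout follow-up.

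**2. What AIC compares.** AIC = 2p − 2 log L. With four arms and a common shape, the Weibull, log-normal and log-logistic models each have p = 5 (intercept, three treatment terms, one shape); the exponential has p = 4. Among the first three, AIC simply ranks the likelihood, to which baseline shape contributes. Nothing in it tests whether the treatment effect is constant.

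**3. How often a proportional-hazards (PH) family wins.** All inputs below are assumptions, and all runs are unweighted with PH tested at 5%.

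| Assumed setting | PH rejected | PH family then chosen |
|---|---|---|
| A. Two arms, n = 30,000, 5 years; delayed benefit (HR 1.0, then 0.8 after year 1) or early harm with late benefit (1.3, then 0.85); Weibull baseline shape 0.9–1.2; exponential, Weibull, log-normal, log-logistic | 42+18+34+59 = 153 of 240 | 34+15+22+42 = 113 of 153 (74%) |
| B. Scenarios of A re-run, about 12% control-arm 5-year risk | 79 of 120 | 40 of 79 (51%); by scenario 5 of 30 to 11 of 13 |
| C. As B, adding arm-specific-shape Weibull, log-normal and log-logistic | 79 of 120 | 0 of 79 |
| D. Four arms of 6,000, common shapes with Gompertz added: delayed effect | 45 of 60 | 44 of 45 (98%) |
| D, waning effect | 49 of 60 | 45 of 49 (92%) |
| D, arm-specific Weibull shapes as truth | 60 of 60 | 60 of 60 (100%) |
| D, log-normal time-ratio model as truth | 22 of 60 | 0 of 22 (0%) |

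The range is 0% to 100%, driven by candidate list, baseline shape and event rate. Row C shows that the candidate list alone can remove the problem.

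In practice the likelihood would be weighted. Unstabilized four-arm weights sum to about 4 × N, so ordinary AIC has no standard justification there, and the plan does not address this.

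**4. Dependence of the scale on the data.** Assume, by inference, that the check is made separately for each of 25 composites and that the checks are independent. If PH is true for all, the chance that at least one leaves Cox is 1 − (1 − α)^25: 22% at α = 1%, 72% at 5%, 93% at 10%. If each check rejects with probability q, the chance of a mix of Cox and parametric models is 1 − q^25 − (1 − q)^25, at least 93% for q from 0.1 to 0.9. The composites share one cohort, so their checks are correlated and these figures probably overstate the chance. A mix of models is also not always a mix of scales, because exponential and Weibull fits can be reported as hazard ratios.

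**5. The target.** Write expected utility in class *a* as U_a = Σ w_j·E[Y_j(a)], with Σ w_j = 1. The target is U_a − U_b. Even for a single endpoint under Cox, risk by time τ is 1 − S₀(τ)^HR, so a difference needs both S₀(τ) and τ. The plan fixes no horizon and has no step from a hazard or time ratio to U_a − U_b. This holds whichever model is selected.

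**The case against.** The strongest reply is that the text is an overview of an exempt claims analysis inside a minimal-risk interview protocol, where a candidate list would not be expected. The plan does not exclude flexible parametric models, and it promises model diagnostics that could expose a poor fit. That answers several stronger readings a reader might infer:

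- *The fallback usually restores proportional hazards.* Not supported. The frequency depends on inputs that the documents do not give, and it fell to 0 of 79 once arm-specific shapes were allowed.
- *The fallback will certainly be used.* Not supported. No sample size, event count or test is stated. Even the deliberately non-proportional settings in row A rejected in 153 of 240 data sets (64%), and in only 18 of 60 in one scenario.
- *Mixed scales defeat an aim of comparing composites.* Not supported. The plan compares classes within each composite. One model covers all treatment groups, so the six contrasts for a composite share a scale. Comparing effects across composites is not a declared aim.
- *The switch causes the mismatch with the target.* It does not. The mismatch would remain if Cox were used every time.
- *The intervals ignore the pre-test and the selection.* The plan states no interval method, so this can be asked but not asserted.

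What the reply does not answer is that the stated rule, AIC, does not address the failure that triggers it, and that the reported quantity is not the declared one. This is the only analysis plan in the documents, and nothing elsewhere in it closes either gap.

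**Conclusion.** The point holds in a limited form. After proportional hazards is rejected, the plan permits a model that assumes it again, or one that imposes a constant time ratio. That follows from the text and the algebra and needs no simulation. Its frequency is unknown: 0% to 100% of rejections on assumed, unweighted inputs, and no single figure in that range should be quoted as the expected rate. The reported scale therefore depends on the data; that it could differ between composites rests on the inference that the model choice is made for each composite.

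The mismatch between the reported ratios and the declared utility differences is independent of the switch, rests on no simulation, and is the firmer of the two findings. Together they are more than missing detail and should be corrected before outcomes are examined.

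**What to change.** For every composite, make the primary estimate the weighted or targeted-learning expected utility in each class at one horizon, fixed before outcomes are examined. Report the six pairwise differences with bootstrap or influence-curve 95% confidence intervals. This estimates the plan's own target and removes the test-then-select step from the primary analysis.

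Keep the weighted Cox hazard ratio as a descriptive summary. If a parametric model is retained as secondary, list its candidates in advance and include some that let the treatment effect vary over time, such as arm-specific shapes.

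The cost is analysis-plan wording and programming. The small downside is that follow-up beyond the chosen horizon does not enter the primary contrast.

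### One paragraph of the plan makes estimation of the pairwise effects conditional on a significant omnibus test, while the next estimates all six without condition

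*Combined protocol and SAP*

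**What the plan says.** All the relevant text is in the Data Analysis Plan of the combined protocol and SAP, in the part that outlines the claims-data (OLDW) analysis.

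- **Target.** The quantitative-analysis text compares the four drug classes "with respect to each of these patient-specified composite outcomes" and adds: "The target parameter will be the six pairwise differences in the personalized utility function between the drug classes".
- **Time-to-event paragraph, reporting.** For the final weighted model, the plan will report "either hazard or time ratios with 95% confidence intervals". No condition is attached, and the pairs covered are not listed.
- **Time-to-event paragraph, gate.** The four classes are fitted jointly, and on that fit "the omnibus test for at least one treatment group having a different cumulative incidence rate will be evaluated". The rule that comes next is the one at issue: "If that test is statistically significant, then each pairwise comparison will be tested and pairwise effects estimated".
- **Targeted-learning paragraph.** Hazard or time ratios "will be estimated for each of the 6 pairwise comparisons between treatment groups". The following sentence sets an omnibus test of equal hazard rates at 0.05, with Holm-adjusted pairwise p-values. It does not say that the omnibus result decides whether anything is estimated or tested.

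No sentence says what is reported for a composite whose omnibus test is not significant.

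**The concern.** Gating hypothesis tests behind an omnibus test is ordinary practice. Gating the estimates is different, and the time-to-event paragraph does both in one sentence.

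The protocol's question is which class is best for the outcomes that an individual patient wants. For some composites the useful answer may be that the classes hardly differ, and the evidence for that is a set of ratios near 1 with narrow intervals. If those are not produced because the omnibus test was not significant, a reader cannot separate close similarity from too little information. The pairwise effects that do appear will have passed a significance filter, which tends to push them away from 1 and makes their nominal 95% CIs unreliable.

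An analyst who follows the targeted-learning paragraph avoids both problems. What is reported therefore depends on which of two adjacent paragraphs is followed.

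**Working it through.** **1. Number of pairs.** Four classes give 4 × 3 / 2 = 6 pairs, which matches the plan's own six.

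**2. What is reported after a non-significant omnibus test, for one composite.**

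| Rule followed | Pairwise ratios with CIs |
|---|---|
| Targeted-learning paragraph | all 6 |
| Time-to-event paragraph, reporting sentence honoured | not stated; at least those that the final model reports |
| Time-to-event paragraph, gate sentence alone | none |

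The middle row cannot be filled in from the text. A four-group model is often printed as three ratios against a reference class, but the plan names no reference class for the treatment comparison. If only three were printed, the other three point estimates would follow by division (B vs C = B vs A ÷ C vs A). Their CIs would not, because they also need the covariances.

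**3. What selection on the omnibus test does in general.** The documents give no claims-data sample size, event count or effect size, so this is an illustration under assumptions:

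- four independent normal class estimates x₁,…,x₄, each with standard error (SE) 1;
- three classes with mean 0 and one with mean m;
- omnibus statistic Q = Σ(xᵢ − x̄)², significant if Q exceeds 7.81 (the 95th percentile of chi-square with 3 df);
- results taken only from runs with a significant Q, 2,000,000 runs per scenario.

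The non-centrality of Q is m² × 3/4, so m = 2 gives 3 and power of about 27%. Exaggeration is (mean gated contrast ÷ m) − 1. At m = 2 the mean gated contrast is 3.22, and 3.22 / 2 − 1 = 61%.

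| m | Omnibus power | Mean exaggeration | 95% CI coverage, equal pairs | 95% CI coverage, different pairs |
|---|---|---|---|---|
| 2 | 27% | 61% | 87% | 90% |
| 3 | 57% | 24% | 92% | 95% |
| 4 | 84% | 8% | 94% | 96% |
| 5 | 97% | 2% | 95% | 96% |
| 6 | 99.6% | 0.2% | 95% | 95% |

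The CIs are unadjusted.

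With all four classes equal (m = 0), the gate opens in 5% of runs, whatever the sample size. In those runs an unadjusted 95% CI for a pair covers 63%, and the mean absolute contrast is 1.57 SE, against 0.80 SE without the gate.

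**4. Is the gate needed for error control?** In a separate run of 400,000 with all classes equal, the chance of any Holm rejection among the six pairs was 0.041 without the gate and 0.038 with it. In that setting Holm alone holds 0.05 within one composite.

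**The case against.** The strongest case is that the two paragraphs describe one procedure. The first gives the sequence (one model, omnibus test, pairwise comparisons). The second names the estimator, the 0.05 level and the Holm adjustment, and speaks of a single overall test. Read with the unconditional promise of ratios and CIs, the plan as a whole leans towards giving estimates whatever the omnibus result. This reading is reasonable, but the text does not settle it. The targeted-learning paragraph states estimation first, without condition, and the if-then sentence still covers estimation.

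It is also fair that the claims analysis is introduced as an overview, and that a fuller plan may exist elsewhere. That excuses missing detail. It does not remove a rule that is stated.

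Some stronger readings are tempting, and the documents do not support them:

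- **Exactly three, or all six, estimates are lost.** Three assumes a reference-class printout that the plan does not specify, and even then only the CIs of the other pairs would be out of reach. Six requires ignoring both the reporting sentence and the targeted-learning paragraph.
- **The gate suppresses the declared target parameter.** The target is six utility differences, whereas the gate is written for a time-to-event model and its ratios. No gate on the utility differences is stated. The target supports reporting all six comparisons, but the contradiction lies between the two later paragraphs.
- **There are two rival omnibus tests with different nulls.** One sentence speaks of cumulative incidence and the other of hazard rates, but "If the proportional hazards assumptions hold, this will be a Cox model", and under that model the two nulls are essentially the same. Which estimator supplies the test is worth a clarifying clause and is not a separate fault.

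**Conclusion.** The inconsistency is real and narrow, and the wording should be corrected. One sentence makes pairwise estimation depend on a significant omnibus test; the adjacent paragraph does not. Followed literally, the first would leave a composite with a non-significant omnibus test without some or all of its six pairwise estimates and CIs, and would select the reported effects on significance.

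The size of the distortion in this study is unknown. The figures above rest on independent normal estimates, equal precision and assumed effects, and they matter only if estimates really are withheld. They should not be read as predicted bias for the OLDW analysis. If the classes differ and power is very high, the distortion is negligible. If the classes are truly equal, more data do not help, because the gate stays shut 95% of the time.

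**What to change.** Replace the gate sentence in the time-to-event paragraph with wording such as:

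> All six pairwise effects (hazard or time ratios, according to the model) will be estimated and reported with 95% CIs for every composite whatever the omnibus result; the omnibus test, if kept as a gate, applies only to the Holm-adjusted significance tests.

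Make the targeted-learning paragraph consistent with it. If the gate is kept, add a clause saying whether the omnibus test comes from the weighted model or from the targeted-learning analysis. Dropping the gate and relying on Holm alone would also reconcile the two paragraphs.

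The cost is slightly more reporting. No extra data are needed, because the six ratios are contrasts of the four-group model already fitted. If a gate is kept on the tests, error control is unchanged.
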